The study is designed as a prospective, multi-center, randomized, single blinded, controlled study. Patients will be enrolled at a maximum of seventeen (17) centers. Patients will be evaluated pre-operatively and at 6 weeks, 3 months, 1 year, 2 years and annually thereafter until the last patient entered into this study has completed their 2-year evaluation.

STUDY GROUPS AND TREATMENTS

Patients will be randomized to either the Comprehensive® Shoulder System with nano humeral component (investigational) or the Comprehensive® Shoulder System with mini stem component (control) group. Patients will be randomized using a 1:1 (Investigational: Control) blocked randomization plan. The treatment assignment will be revealed intraoperatively. Every attempt will be made to blind patients to their treatment until the end of the study. If a patient is revised or withdraws consent and at the request of the patient, blinding may be discontinued as no further data will be collected.

NUMBER OF PROCEDURES

A total of 264 subjects will be enrolled in this study (132 Control and 132 Investigational).

SELECTION OF SUBJECTS

All subjects considered for participation in the study will be assessed according to predetermined eligibility criteria, listed below. All subjects considered for enrollment must be

recorded on the Subject Screening Log (see Exhibit 11), including patients who are considered but not consented, consented but not randomized and consented and randomized.

Inclusion Criteria

- Patients with non-inflammatory degenerative joint disease including osteoarthritis.
- Patients where the device will be used in the correction of a functional deformity, specifically deformities that prevent congruent articulation of the glenohumeral joint. Examples include but are not limited to: humeral head structural deformity, osteophyte formation restricting range of motion, etc.
- Patients with pain and/or loss of function in the shoulder for whom other treatment modalities have been unsuccessful. Examples include but are not limited to: activity modification, physiotherapy, and anti-inflammatory or other types of medication.
- Patients requiring unilateral or staged bilateral shoulder arthroplasty

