Missing Data: Patients who refuse to return for follow-up or who cannot be located and/or do not formally withdraw consent are described as "missing data." Sites will be instructed to continue efforts to contact these patients. See Statistical Plan for more information on how missing data will be handled in the analysis.

Osteolysis: As defined in Exhibit 3: Radiographic Protocol.

Other Interventions: This category includes other surgeries the patient incurs while enrolled in the study that are seemingly unrelated to the implanted device. This would include surgeries such as cholecystectomy, appendectomy, coronary artery bypass surgery, etc.

Revision: A procedure that removes part of the original implant configuration, with or without replacement of the entire component configuration.

Removal: A procedure where the entire original system configuration is removed.

Reoperation: Any surgical procedure that does not include removal or revision, for example, drainage of a hematoma at the surgical site.

Screen Failure: A patient who is either screened but not consented, consented but not randomized or randomized but does not receive the investigational or control device.

Adverse Event (AE): Any event occurring in a study subject that, in the opinion of an M.D. or other qualified and trained medical professional, represents an untoward medical occurrence that differs in either nature, severity, or frequency from a normal post-operative finding. AEs may not have an apparent causal relationship with the device. An AE can therefore be any discrete or ongoing unfavorable and unintended sign (including an abnormal laboratory finding), symptom, or disease temporally associated with the use of a product.

Serious Adverse Event: Any untoward medical occurrence that:

- Results in death
- Is life-threatening
- Requires in-patient hospitalization* or prolongation of existing hospitalization
- Results in persistent or significant disability/incapacity
- Results in congenital anomaly/birth defect

*A planned hospitalization for a pre-existing condition, or a procedure required by the protocol, without a serious deterioration in health is not considered to be a serious adverse event.

Unanticipated Adverse Device Event: any serious adverse event that is or may possibly be related to the device other than those listed in Section C: Risk Analysis or in the institution's approved Informed Consent.

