A significant disability is one that causes substantial disruption to the person's normal life and activity.

The investigator or designee must complete the SAE reporting (SAE100). Then relative to the event, a Revision/Removal Form (RR 100), and/or the Withdrawal Form (WD100) form should be completed. See the Implant Retrieval and Analysis of Removed Implants section below for instructions on how to handle investigational devices that are removed from study subjects.

DISCONTINUATIONS AND REVISIONS (SUBJECT WITHDRAWAL)

It is recognized that the subject's participation in this trial is entirely voluntary, and that she/he may refuse to participate and may withdraw from participation at any time without jeopardy to any future medical care. Device Revision or Removal is also considered a withdrawal event when all components are removed, or if only the humeral stem is removed. No additional study follow-up is necessary. In the event that a patient receives a partial revision (not all components/humeral stem), a revision/removal form should be completed, but the patient should still be followed per protocol. Do not complete a withdrawal form for these patients. *Enrollment for this study is defined as receipt of either a control or an investigational device.*

Therefore:

- Subjects withdrawn from the study after receipt of either the control or investigational device will NOT be replaced.
- Randomized patients who do not ultimately receive the control or investigational device:
 - 1. *WILL* be replaced, but
 - 2. Randomization assignment will not be re-used
- *All* subject withdrawals must be documented on the Withdrawal Form (WD100).

- Includes randomized patients who do not ultimately receive the control or investigational device configurations.
- If withdrawal is due to device removal or revision, the SAE 100 form must be completed. The Revision/Removal form (RR 100) should be completed in all cases including device removal details, if known.

Copies of all Case Report Forms are included in Exhibit 4.

CONTROL OF INVESTIGATIONAL DEVICE

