The three co-primary endpoints for this study are:

- a. ASES score at 22+ Months
- b. No unanticipated device-related adverse event, and no fracture, perforation of the bone or joint dislocation, and no fracture, perforation or dissociation of the device, and no revision or removal of any component, and
- c. Radiographic Success, as defined by:
 - a. Subsidence of the humeral component < 5 mm, and
 - b. Migration of the humeral component < 5mm, and
 - c. No progressive lucency around the humeral component >2mm in two or more contiguous zones
 - d. Migration of the glenoid component <5 mm, and
 - e. No progressive lucency >2mm around the entire glenoid component

SECONDARY ENDPOINTS

The data collected will also be analyzed for the following secondary endpoints:

- 1. American Shoulder and Elbow Surgeon's Score (ASES) at all time points
- 2. Single Assessment Numeric Evaluation (SANE) Score at all time points
- 3. Constant Score at all time points, except 6 weeks (adjusted for age and gender)
- 4. Radiographic assessment of radiolucencies and subsidence
- 5. Overall adverse events including removal/revision and other serious adverse events

The safety of the system will be monitored by recording adverse events including serious adverse events not considered UADEs throughout the follow-up period. Types of events to be collected include but are not limited to:

- Device removal or revisions
- Unanticipated adverse device events
- Systemic adverse events
- Local adverse events
- Reoperations and Other Interventions

Study participants will only be considered discontinued/withdrawn for the following reasons:

- Death
- Withdrawal of consent (written)
- Revision/Removal

Information from any patient who fails to return for multiple, consecutive, scheduled follow-up visits for any reason other than the criteria listed above will be identified as Missing Data.

ANTICIPATED CHANGES

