Theoretically Due: The number of implants that could be examined if all subjects returned on the first day of the follow-up window based on their respective initial surgery dates and the date of database closure.

Deaths: The number of deaths that have taken place in the course of the investigation according to scheduled follow-up visits.

Revisions: The number of revisions that have taken place in the course of the investigational study recorded according to the scheduled follow-up visit.

Withdrawal of Consent: The number of subjects that have withdrawn during the course of the investigational study recorded according to the scheduled follow-up visit.

Not Yet Overdue: Subjects in this category are those who have not yet been evaluated but who are still within the evaluation time window at the time of database closure.

Actual^A: The number of subjects with complete data (i.e. all primary outcomes can be determined) who are actually evaluated within the protocol-defined follow-up intervals.

Actual^B: The number of subjects with any follow-up data (in- or out-of-window) reviewed or evaluated by investigator ("all evaluated" accounting).

Expected: This element is the number of subjects expected for a given time interval. These include the theoretical number of subjects who are due to be evaluated, less the number of subjects who have died, withdrawn, been revised, or are not yet overdue in this time interval.

Follow-up Rate: This element is the ratio of actual subjects evaluated to expected subjects, expressed as a percentage.

MODELS FOR CONTINUOUS MEASURES

Comparisons of Investigational vs Control with regard to continuous baseline and secondary outcomes will be performed using standard statistical tests and will be chosen as appropriate for the scale and distribution of the measures being analyzed. A t-test, Wilcoxon test, or oneway ANOVA (as appropriate) will be performed to assess differences.

CATEGORICAL DATA ANALYSES

Comparisons of Investigational vs Control with regard to categorical baseline, secondary and safety outcomes will be performed using standard statistical tests and will be chosen as appropriate for the scale and distribution of the measures being analyzed. Specifically, categorical outcomes will be compared for investigational and control groups using the Fisher's Exact test (for 2x2 tables) or the Likelihood Ratio chi-square test (for tables larger than 2x2).

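### The unblinding and follow-up accounting rules treat every revised patient as finished, but partially revised patients stay in follow-up and keep giving ASES scores

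*Combined protocol and SAP*

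**What the plan says.** Five places in the combined protocol and SAP bear on a patient whose implant is revised.

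- **Study Groups and Treatments (Section B).** Sites are to try to keep patients blinded to the end of the study. If a patient is revised or withdraws consent, and asks, "blinding may be discontinued as no further data will be collected".
- **Study Definitions and Glossary.** A revision is "A procedure that removes part of the original implant configuration, with or without replacement of the entire component configuration". Withdrawal is narrower: death, written withdrawal of consent, or removal of all components or of the humeral stem components.
- **Discontinuations and Revisions (Subject Withdrawal).** This agrees with the glossary. After a revision that spares the humeral stem and is not complete, "a revision/removal form should be completed, but the patient should still be followed per protocol", and sites are told not to file a withdrawal form.
- **Secondary Endpoints, closing list.** "Study participants will only be considered discontinued/withdrawn for the following reasons": the list gives death, written withdrawal of consent, and revision/removal, with nothing said about partial revision.
- **Subject Accounting.** Expected is the number theoretically due, "less the number of subjects who have died, withdrawn, been revised, or are not yet overdue in this time interval". The second Actual count takes anyone with any follow-up data. The first takes those with complete data within the visit window.

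The visit schedule collects the ASES at every follow-up visit, and the ASES at 22+ months is a co-primary endpoint. The inclusion criteria require patients to agree to stay blinded until the 22+ month evaluations are done.

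**The concern.** The permission to unblind rests on one stated reason: data collection is over. For a partially revised patient it is not. Such a patient may learn the assignment and then complete the ASES, which the SAP treats as patient-reported when it justifies the margin. Blinding the patient is meant to protect exactly that kind of outcome.

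The case is realistic. The Introduction names glenoid loosening as the most common reason for revising a total shoulder, and a glenoid revision that leaves the humeral stem in place is a partial revision under this protocol.

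Two further matters follow. The sections disagree on whether a partially revised patient has left the study. And the follow-up rate, which readers use to judge the completeness of the data, can count in its numerator people it has removed from its denominator.

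**Working it through.** **Step 1. The texts side by side, for a patient with a partial revision.**

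| Section | Status of the patient |
|---|---|
| Study Groups and Treatments | Revised; may be unblinded on request; no more data expected |
| Secondary Endpoints list | Discontinued/withdrawn |
| Glossary, Withdrawal | Not withdrawn |
| Discontinuations and Revisions | Not withdrawn; all scheduled visits continue |
| Subject Accounting, Expected | Subtracted |
| Subject Accounting, Actual | Counted if seen |
| Analysis Population | Included (revision at or before 26 months, or complete data) |

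The first two rows conflict with the third and fourth. The fifth and sixth conflict with each other.

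**Step 2. The plan's own ASES figure.** Inputs from the ASES sample size section: margin 9.5, SD 19, one-sided α 0.05, power 90%. The normal approximation is n = 2(z₀.₉₅ + z₀.₉₀)² × SD²/margin² = 2 × (1.645 + 1.282)² × 19²/9.5² = 2 × 8.567 × 4 = 68.5, so 69 per arm. The noncentral t calculation gives 70 per arm (power 0.903), which is the plan's figure, and 70/0.85 = 82.4 gives its 83. Nothing in this point changes these numbers.

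**Step 3. How many shoulders.** The sample size section for Absence of Revision/Removal/UADE uses a revision rate of 2.0%. Then 0.02 × 132 = 2.6 shoulders per arm and 0.02 × 264 = 5.3 in all. That is the ceiling for partial revisions at this rate; the documents do not give the partial share.

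**Step 4. How far an arm mean could move.** Shift in arm mean = revision rate × partial share × change in an individual's score after unblinding. The share (50 to 100%) and the change (10 to 30 points) are assumptions. Every partially revised patient is taken to be unblinded, to have a later score analysed, and to shift in the same direction.

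| Revision rate | Lowest (50%, 10 points) | Highest (100%, 30 points) |
|---|---|---|
| 2% (plan) | 0.02 × 0.5 × 10 = 0.1 | 0.02 × 1 × 30 = 0.6 |
| 5% (assumed) | 0.05 × 0.5 × 10 = 0.25 | 0.05 × 1 × 30 = 1.5 |

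Against the margin, 0.6/9.5 = 6% and 1.5/9.5 = 16%.

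**Step 5. The follow-up rate.** Follow-up rate = Actual/Expected. A partially revised subject who attends adds 1 to Actual and takes 1 from Expected. With 264 due, 5 partially revised and attending, and no other subtraction, the denominator is 259 instead of 264, so the rate is overstated by a factor of 264/259 = 1.02.

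**The case against.** The strongest reply is that the protocol already limits the damage. Unblinding is permitted, not automatic, and only when the patient asks; it follows an instruction to keep patients blinded. The explicit instruction on follow-up, in Discontinuations and Revisions, is clear and matches the glossary, so a careful site would keep collecting data. Missing Data and Sensitivity Analyses asks for an ASES before the revision where possible, and that score precedes any unblinding the revision could prompt. The other two co-primary endpoints are largely out of reach: a revised shoulder already fails the revision endpoint, one revised before two years counts as a radiographic failure, and an independent reviewer reads the films.

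All of this stands, and it keeps the point minor. It does not remove it. The SAP does not say whether the pre-revision score or the 22+ month score is analysed when a partially revised patient has both, so the early score does not close the gap.

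A reader might infer that the follow-up rate will exceed 100%. That needs attending partially revised subjects to outnumber missed visits. At the planning rate there are at most about 5, against 0.05 × 264 = 13 missed visits if 5% are missed (assumed). A reader might also infer that subtracting consent withdrawals conceals dropout. The documents do not support that: the denominator is openly defined, contradicts no other section, and the accountability table defines withdrawals as a separate element.

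**Conclusion.** The inconsistency is real. Unblinding rests on a reason that is untrue for patients whom the protocol keeps in follow-up, the discontinuation list contradicts the withdrawal rule, and the follow-up rate has a numerator that is not a subset of its denominator.

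The expected size is small: at most about 5 of 264 shoulders at the plan's 2% revision rate, a movement of roughly 0.1 to 0.6 points in an arm's mean ASES against a margin of 9.5, and about 2% relative overstatement of the follow-up rate. The ASES range rests on the assumed partial share and score shift; at an assumed 5% revision rate it would be 0.25 to 1.5 points. It would be wrong to read this as a threat to the non-inferiority conclusion. No sample size, margin or test is affected. The point is worth making because the wording permits an avoidable loss of blinding before a subjective co-primary score, and the repair is nearly free.

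**What to change.** 1. **Study Groups and Treatments:** allow unblinding on request only once study follow-up of that shoulder has ended.
2. **Secondary Endpoints, discontinuation list:** bring the revision/removal entry into line with the glossary and with Discontinuations and Revisions, so that all three say the same about partial revision.
3. **Subject Accounting:** subtract from Expected only those revised subjects whose follow-up has ended.
4. **Missing Data and Sensitivity Analyses:** state which ASES score, pre-revision or 22+ month, enters the primary analysis after a partial revision. Fix this before any unblinded comparison.

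The cost is a few sentences in one amendment, with the IRB approval that the protocol requires for any change. At the planning rate the reported follow-up rate may fall by about 2%.

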The Comprehensive® Shoulder System with nano humeral component addresses these issues by offering a minimally invasive humeral component that allows the surgeon to recreate the patient's natural humeral head version and inclination, while also allowing unobstructed access to the glenoid. The Comprehensive® Shoulder System with nano humeral component is an evolved design based on the Biomet TESS® shoulder that is currently marketed outside of the United States including Europe and Canada. The Comprehensive® Shoulder System with nano humeral component has a reverse morse taper locking mechanism that allows it to interface with Biomet's current offering of Comprehensive® shoulder components for enhanced flexibility in the surgical suite. The Comprehensive® nano also utilizes Biomet's proven PPS® Porous Plasma Spray technology for proximal fixation.

SECTION A: PURPOSE PURPOSE/OBJECTIVES

The purpose of this clinical investigation is to establish the safety and efficacy of the Comprehensive® Shoulder System with nano humeral component in Total Shoulder Arthroplasty. Safety and efficacy of the device will be measured by collection and analysis of the following data at the two-year or greater time point (22 months post-operative or longer):

- 1. American Shoulder and Elbow Surgeons (ASES) Score
- 2. Single Assessment Numeric Evaluation (SANE)
- 3. Constant Score
- 4. Radiographic assessment of osteolysis, radiolucencies, migration, and subsidence
- 5. Comparison of overall adverse event rates including rates of removal/revision and other serious adverse events.

Please refer to the Statistical Analysis Section for a description of the analyses that will be used.

RATIONALE FOR CURRENT STUDY

The current study is designed to determine the safety and efficacy of the Comprehensive[®] Shoulder System with nano humeral component implants (investigational) by measuring clinical, radiographic and safety outcomes when compared to the Comprehensive[®] Shoulder System with mini stem component (control) at the two-year or later follow-up time point.

The data collected as part of this study will be used to support Pre-Market Notification (U.S.) clearance of the Comprehensive[®] nano Humeral shoulder system and as such will be conducted according to all relevant FDA regulations for IDE clinical trials, sponsor and IRB requirements.

SECTION B: PROTOCOL OVERALL DESIGN

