Complete eligibility checklist	x					
Complete Patient History Form: HX100	x					
Complete ASES Assessments: ASES100	x		х	x	х	х
Complete SANE Assessment: SANE100			x	x	x	х
Complete Constant Score Form: CST100	х		X**	x	х	х
Randomize Patient		х				
Record Operative Details: OP100		х				
Collect Radiographic Images (AP Int., AP Ext, and Axillary Views)			x	x	x	x
Protocol Deviation Form: PD100	As needed	As needed	As needed	As needed	As needed	As needed
Complete Adverse Event Form: AE100 and/or Serious Adverse Event SAE100	As needed	As needed	As needed	As needed	As needed	As needed
Complete patient Withdrawal Form: WD 100		As needed	As needed	As needed	As needed	As needed
Complete Device Revision/Removal: RR100			As needed	As needed	As needed	As needed

Each follow-up visit time point will be determined based on the date of surgery.

** At the 6 week interval, in order to protect the subscapularis repair, the strength and ROM sections are not to be completed by sites.

*** Annual follow up will continue until study closure or until the last enrolled patient reaches their 2 year follow up window.

BILATERAL PATIENTS

A patient undergoing staged bilateral surgery must sign a consent form **for each study procedure**. Each study shoulder will be randomized separately. Bilateral patients will be required to wait at least 9 months between procedures for the purposes of the study.

Patients with staged bilateral study implants will require two ASES, Constant Score, and SANE assessment forms to allow individual assessment of each operative side over the course of the study. Patients must be instructed to assess each shoulder individually, i.e., only record right-shoulder pain levels on the CRF for their right shoulder and only report left shoulder pain on the CRF for the left shoulder.

SCHEDULE OF FOLLOW-UP ASSESSMENTS

Post-operative clinical and radiographic evaluations will be performed according to the following schedule, with the associated visit windows:

- 6 weeks (± 2 weeks)
- 3 months (± 2 weeks)
- 1 year (± 2 months)
- 2 years (± 2 months)
- Annually thereafter* (± 2 months)
- * Until all patients reach the 2-year visit window or the study is closed

ASSESSMENT PARAMETERS AND METHODS

Pre-Operative Visit - Medical History, Demographic Data and Patient Eligibility

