A description of all protocol deviations will be provided. The association between the proportion of subjects with a protocol deviation and device group across investigators will be examined using the Breslow-Day test for homogeneity of odds ratios. Investigators with less than or equal to 3 cases in either treatment will be combined to form a "pooled" investigator for analysis. A significant p-value indicates heterogeneity of odds ratios for the proportion of subjects (Investigational vs Control) with a protocol deviation across investigators, and in this case the proportions of subjects with a deviation will be examined graphically and descriptively by treatment group and site to assess dependency.

DATA COLLECTION

DATA COLLECTION TIME POINTS

Windows for this study will be as follows:

Table 1: Analysis Windows

Interval	Follow-Up Window
	(Days from Surgery)
Preoperative	≤ 0
6 Weeks	28-56
3 Months	78-106
1 Year	304-426
2 Year	669-791
2+ Year	> 791

The principal data collected is described in the following table:

Study Parameter	Data Collected
Demographic and Baseline Measurements	Age, Height, Weight, Gender, Race/Ethnicity, Unilateral/Bilateral, Primary Diagnosis, Prior Treatments, Concomitant Medications
Efficacy Measurements	American Shoulder and Elbow Surgeons (ASES) Score, Constant Score, SANE Score, Radiographic Assessment
Safety Measurements	Revision/Removal, Adverse Events
Study Success Criteria	Study success requires that the Investigational group successfully demonstrate non-inferiority when compared to the Control group for all three of the individual primary endpoints.

Table 2: Principal Study Data

INFERENTIAL METHODS

SIGNIFICANCE LEVELS

The Type I error rate for the primary study analysis will be 0.05.

Comparisons for secondary, exploratory, and safety analyses will use $\alpha = 0.05$, with no adjustment for multiple comparisons. Because no adjustments will be made for multiple

comparisons, secondary, exploratory, and safety endpoints will be reported as exploratory analyses without claims of statistical significance.

SUBJECT ACCOUNTING

Accountability tables will be generated to show, at each study visit, the number of Investigational and Control subjects who might be expected to attend a given visit and the number and proportion who did attend.

The following definitions specify how the subject accountability table tracks subject follow-up for the Control and Investigational arms:

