BASELINE CHARACTERISTICS

Subjects in the Investigational and Control study groups will be compared regarding a list of baseline items, including preoperative ASES and Constant Scores, demographics (age, gender, and primary diagnosis), medical history, and comorbidities.

EFFICACY EVALUATIONS

Primary Endpoint

The confidence intervals used in the analysis of the binary primary endpoints (Radiographic Success and Absence of Revision/Removal/UADE) will be 1-sided, 95% confidence intervals for the difference between proportions in two independent samples. They will be calculated using the Wald method as based on a normal approximation to the binomial, as follows:

$$(p_C - p_I) + z_\alpha \sqrt{SE_C^2 + SE_I^2}$$

Where

 p_{C} = proportion of success in the Control group, p_{I} = proportion of success in the Investigational group, α = 0.05, and

$$SE_C = \sqrt{\frac{p_C(1-p_C)}{n_C}}$$
 and $SE_I = \sqrt{\frac{p_I(1-p_I)}{n_I}}$

The confidence interval used in the analysis of the continuous primary endpoint (ASES Score) will be a 95% confidence interval for the difference between means in two independent samples. They will be calculated using the normal distribution, as follows:

$$(\overline{x}_C - \overline{x}_I) + z_\alpha \sqrt{\frac{s_C^2}{n_C} + \frac{s_I^2}{n_I}}$$

Where

 x_{C} = mean ASES score in the Control group,

 $\overline{x_{I}}$ = mean ASES score in the Investigational group,

 $s_{\scriptscriptstyle C}$ = standard deviation of the ASES scores for the Control group,

 s_{T} = standard deviation of the ASES scores for the Investigational group, and

 $\alpha = 0.05$

Secondary Endpoints

Secondary outcomes include the ASES score, SANE score, Constant score, and radiographic endpoints at 6 weeks, 6 months, 1 year, and 2 years separately. These outcomes will be compared for Investigational and Control groups at each time point.

Exploratory Analyses14

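### SANE is a stated efficacy measure but is first collected after surgery, so it alone of the three clinical scores has no baseline; the planned comparison stays valid, but SANE improvement cannot be reported

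*Combined protocol and SAP*

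**What the plan says.** Section A (Purpose/Objectives) introduces its list of measures with "Safety and efficacy of the device will be measured by collection and analysis of the following data", and SANE is the second of five items. Section B (Secondary Endpoints) lists "Single Assessment Numeric Evaluation (SANE) Score at all time points". The SAP's table of principal study data gives the efficacy measurements as "American Shoulder and Elbow Surgeons (ASES) Score, Constant Score, SANE Score, Radiographic Assessment".

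The visit schedule is Table 1 of Section B (Patient Management). The rows "Complete ASES Assessments: ASES100" and "Complete Constant Score Form: CST100" are marked pre-operatively and at each follow-up visit, with a partial Constant form at 6 weeks. The row "Complete SANE Assessment: SANE100" has no pre-operative or intra-operative mark and begins at 6 weeks.

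The SAP's Baseline Characteristics section agrees with that schedule. It compares the arms on items "including preoperative ASES and Constant Scores" and does not name SANE. No section schedules a pre-operative SANE.

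**The concern.** The plan relies on three clinical scores, and two of them have a pre-operative value. No reason is given for treating SANE differently, and a pre-operative score cannot be obtained once the shoulder has been replaced.

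Three things are at stake for SANE:

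- Improvement from baseline cannot be reported for either arm.
- A chance difference between arms in pre-operative SANE itself would go unseen.
- The SANE comparison cannot be adjusted for the score's own baseline, so any precision from that adjustment is lost.

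**Working it through.** The plan states no figure on this point, so the first step is a comparison of entries.

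**Step 1. The three rows of the visit schedule (Section B, Table 1).**

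| Score | Pre-op | Intra-op | 6 weeks | 3 months | 1 year | 2 years and annually |
|---|---|---|---|---|---|---|
| ASES | x | – | x | x | x | x |
| SANE | – | – | x | x | x | x |
| Constant | x | – | x (partial) | x | x | x |

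A mark lost in reading the table is unlikely. All four later SANE marks are in place, and Baseline Characteristics independently omits SANE. The case report forms (Exhibit 4) were not available to check.

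**Step 2. What the plan does with baseline scores.**

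- SANE: compared between arms at each time point (SAP, Efficacy Evaluations, Secondary Endpoints). The time points listed there are all post-operative. No change score or baseline adjustment is planned.
- Constant: adjusted for age and gender. No adjustment for pre-operative Constant is stated.
- ASES: the co-primary analysis is an unadjusted difference in means. Pre-operative ASES is a covariate only in the exploratory regressions of the primary endpoints, and ASES change is used only in the exploratory analysis against radiographic findings.

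So no analysis now planned fails for want of a SANE baseline.

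**Step 3. Size of the lost precision.** Let r be the correlation between pre-operative and follow-up SANE. The documents give no value; 0.2 to 0.5 is an assumption. Three formulas are used:

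- Adjusting for baseline multiplies the variance of the between-arm difference by 1 − r².
- With 112 evaluable shoulders per arm (the SAP's number before the attrition allowance), the two-sided 95% half-width in SD units is 1.96 × √(2/112 × (1 − r²)). With no adjustment it is 1.96 × √(2/112) = 0.262.
- An unadjusted change score, with equal SDs before and after, has variance 2(1 − r) times that of the follow-up score.

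| r (assumed) | 1 − r² | Variance cut | Half-width (SD) | Change-score ratio 2(1 − r) |
|---|---|---|---|---|
| 0.2 | 0.96 | 4% | 0.257 | 1.6 |
| 0.3 | 0.91 | 9% | 0.250 | 1.4 |
| 0.4 | 0.84 | 16% | 0.240 | 1.2 |
| 0.5 | 0.75 | 25% | 0.227 | 1.0 |

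Two readings follow. First, the 4% to 25% is measured against no adjustment at all. Pre-operative ASES and Constant are already collected, so for a given r it should be read as an upper bound on what a SANE baseline would add. Second, an unadjusted change score is more precise than the follow-up score only if r exceeds 0.5. Change should therefore be descriptive, and the adjusted difference should carry the comparison.

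**Step 4. Effect on sizing.** None. The sample size comes from the three co-primary endpoints, and SANE plays no part in it.

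**The case against.** The strongest reply is that this is a consistent design choice. Section A ties SANE to data at 22 months or later, the schedule and the baseline section agree with each other, and no SANE change or baseline-adjusted analysis is promised. The SAP's Significance Levels section reports secondary endpoints as exploratory, without claims of significance. All of that stands, and it limits how far the point can be taken. Four stronger readings are tempting but are not supported:

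- **That the SANE comparison is biased or unusable.** Randomization keeps the post-operative comparison between arms valid.
- **That imbalance in starting condition cannot be seen or adjusted for.** Pre-operative ASES and Constant are scheduled for every shoulder and compared between arms, and both could serve as proxy covariates. Only imbalance specific to SANE is hidden. The proxies are partial: entry requires ASES of 40 or less, which narrows the range of that score, and neither can give SANE change.
- **That SANE loses an adjustment which the other two scores receive.** As step 2 shows, the plan does not baseline-adjust the main ASES comparison or the Constant comparison either.
- **That the secondary-endpoint wording contradicts the schedule.** Its reference to every time point can be read as the visits that the schedule sets for SANE, all of which are post-operative.

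The reply does not remove the fact that a named efficacy score cannot be reported as improvement, and that this cannot be repaired after surgery.

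**Conclusion.** The point holds as a low-cost improvement, not as an error in the plan. SANE is the only one of the three clinical scores without a pre-operative value, and this applies to all 264 planned shoulders (132 + 132). Within-patient SANE improvement, a SANE-specific balance check and adjustment for SANE's own baseline are unavailable. The precision at stake is at most 4% to 25% of the variance of the SANE difference. That range rests wholly on the assumed r of 0.2 to 0.5, and restricting entry by ASES would tend to lower r. Study success depends only on the three co-primary endpoints, so the primary conclusion does not change.

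**What to change.** 1. In the protocol's visit schedule (Section B, Table 1), mark SANE100 in the pre-operative column, to be completed with the pre-operative ASES.
2. In the SAP's Baseline Characteristics section, add pre-operative SANE to the scores compared between arms.
3. In the SAP's Secondary Endpoints section, report the between-arm SANE difference at each visit adjusted for pre-operative SANE, and give change from baseline by arm as a descriptive summary.

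The cost is one short added assessment at a visit that already collects ASES and Constant, plus an update to the case report form schedule. Shoulders operated on before the change would lack the value, so the report should state how many have it. Adjusting SANE would also give an exploratory score a fuller analysis than the co-primary ASES comparison receives; that is acceptable if it is labelled exploratory. No sample size, power figure or co-primary analysis changes.
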